7.4 Primary Endpoint Analysis

The primary endpoint will be analyzed by assessing the difference in the change of BOLD fMRI contrast related to the aggressive response in the PSAP Task from baseline (Visit 2) to the end of treatment (Visit 5) in each treatment group. The completed population will be used for the primary endpoint analyses.

7.4.1 Imaging Analysis

All functional imaging data will be analyzed using statistical parametric mapping software SPM12 package (Wellcome Trust Centre for Neuroimaging, Institute of Neurology; London, UK), Analysis of Functional Neuroimages (AFNI, NIH, USA) and software developed in-house at [name] lab, by [name], and at Supernus. Additional software that may be used includes FSL (Oxford, Cambridge, UK), Freesurfer (MGH, USA), and Matlab (MathWorks, USA). While performing the PSAP Task, neuronal activation is anticipated in the ACC, ventromedial PFC, amygdala, insular regions, and ventral striatum including nucleus accumbens, etc. Therefore these ROIs will be emphasized on the imaging analysis.

7.4.1.1 PSAP Task

For the PSAP Task data, the analyses will be mainly descriptive and will be assessed as the change in BOLD fMRI contrast associated with the aggressive response at baseline and post-treatment. The primary endpoint may be analyzed (depending on the data availability) by assessing the mean, SD, median, minimum and maximum of the BOLD signal change related to aggression for each treatment group (SPN-810 36 mg group and placebo) and study visit (baseline and Visit 5).

7.5 **Secondary Endpoint Analyses**

The secondary endpoint analyses will be based on the completed population.

7.5.1 Functional Connectivity (Resting State fMRI)

The secondary endpoints for functional connectivity will be the actual z-score, converted from the Fisher's Z-transformation of correlation coefficients, acquired during the rs-fMRI at Baseline (Visit 2) and Visit 5.

The analyses of the resting state data will be exploratory and informative of the connectivity between ROIs of the aggression network. Correlation matrices representing functional connectivity in the aggression network for each resting state scan will be generated at Visit 2 (baseline) and at Visit 5. The correlation values will be converted to a z-score (Fisher's Z-transformation). The descriptive analyses will be performed to assess the z-scores by treatment group (SPN-810 36 mg group and placebo) and visit (baseline and Visit 5).

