against a fictitious opponent located in a different building. The subject can steal points (simulating an aggressive behavior) or have points stolen by the opponent (i.e., provocation). At the beginning of the task, subjects will be instructed that they and their opponent could earn as many points as possible that can be turned into money. The subject can press 1 of 3 buttons on a keypad (Option 1, 2 or 3) a set number of times to achieve a specific outcome.

BOLD fMRI

BOLD (blood oxygenation level-dependent) fMRI is a method used to investigate brain activity by measuring the change in blood oxygenation. When a brain area is active, the flow of oxygenated blood increases to that region in response to increased oxygen demand. Changes in the relative levels of oxyhemoglobin and deoxyhemoglobin can be detected due to their differences in magnetic susceptibility. Deoxygenated hemoglobin is paramagnetic while oxygenated hemoglobin is diamagnetic. An Echo Planar Imaging (EPI) MRI sequence is sensitive to changes in magnetization (T2*) and can therefore be used to measure blood oxygenation as a proxy for brain activity during the task.

BOLD Resting fMRI

A resting-state BOLD fMRI (rs-fMRI) will be measured (subjects will look at the image of a crosshair during an 8-minute scan) after the completion of the PSAP Task fMRI and MR spectroscopy. The rs-fMRI will be used to identify functional connectivity in brain networks in subjects "at rest." Connectivity is measured by the spontaneous fluctuations in the BOLD signal. The more synchronized these fluctuations are, the more connected the brain regions.

Randomization (Visit 3):

After the completion of the baseline procedures, eligibility will minimally require completion of (1) two PSAP sessions and (2) the MPRAGE structural scan. Eligible subjects will be randomized in a 1:1 ratio to receive placebo or 36 mg/day SPN-810 and will proceed to the Treatment Phase.

Treatment Phase:

Subjects will be titrated for 2 weeks and the final dose will be maintained for 2 weeks. Subjects will return for PK sampling at Visit 4.

At the end of the Maintenance period, subjects will return to the Imaging Center to complete the post-treatment MRI session with the same MR imaging acquisition procedures as performed at the Baseline MRI session. The visit (Visit 5) will be scheduled within 3 hours +/- 1 hour from the time the dose of study medication was taken.

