All functional imaging data will be analyzed using statistical parametric mapping software SPM12 (Wellcome Trust Centre for Neuroimaging, Institute of Neurology; London, UK), Analysis of Functional Neuroimages (AFNI, NIH, USA), and in-house software developed in [name] lab at Northwestern University, Chicago, by [name], and at Supernus. Additional software that may be used includes FSL (Oxford, Cambridge, UK), Freesurfer (MGH, USA), and Matlab (Mathworks, USA).

While performing the PSAP Task, neuronal activation is anticipated in the ACC, ventromedial PFC (VmPFC), amygdala, insular regions, and ventral striatum including the nucleus accumbens, etc. Therefore these regions of interest (ROIs) will be emphasized during the imaging analysis.

Primary Analysis:

Both primary and secondary analyses will be based on the completed population.

The primary endpoint will be analyzed by assessing the difference in the change in BOLD fMRI contrast related to the response to the PSAP Task from Baseline (Visit 2) to Visit 5 between each treatment group (SPN-810 36 mg group and placebo).

Secondary Analysis:

Secondary endpoints will be the difference in the change in functional connectivity values (Fisher's Z-transformation of the correlation coefficient) between relevant brain regions obtained during resting state, from Baseline (Visit 2) to Visit 5 between each treatment group (SPN-810 36 mg group and placebo). The relevant variables for the correlation matrices will be calculated by Northwestern University.

Concentrations of GABA and Glu in the ACC will be analyzed descriptively. The statistics will be assessed by treatment group, at Baseline (Visit 2) and at Visit 5. The 2-sided 95% CI for the mean difference between two treatment groups, pre- and post-treatment will be examined.

Details of the analyses will be provided in the SAP.

Safety Analysis:

Safety analysis will be based on the safety population. All AEs will be coded using the Medical Dictionary for Regulatory Activities (MedDRA) and will be summarized at subject and event levels by System Organ Class (SOC), Preferred Term (PT), and study treatment. The treatment-emergent AEs will be analyzed similarly by severity, and study drug relatedness. The descriptive statistics will be summarized for continuous measures, and percentage will be reported for categorical measures from the clinical laboratory results, AEs, vital signs, ECGs, and findings from the physical examinations.

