8.2 Secondary Endpoint Analyses

8.2.1 Functional Connectivity (Resting State fMRI)

The secondary endpoints for functional connectivity will be the actual z-score, converted from the Fisher's Z-transformation of correlation coefficients, acquired during the rs-fMRI at Baseline (Visit 2) and Visit 5.

The analyses of the resting state data will be exploratory and informative of the connectivity between ROIs of the aggression network. Correlation matrices representing functional connectivity in the aggression network for each resting state scan will be generated at Visit 2 (baseline) and at Visit 5. The correlation values will be converted to a z-score (Fisher's Z-transformation). The descriptive analyses will be performed to assess the z-scores by treatment group (SPN-810 36 mg group and placebo) and visit (baseline and Visit 5).

The mean difference, of the z-scores between two treatment groups (SPN-810 36 mg group minus placebo) and pre- and post-treatment (post- minus pre-treatment) and the associated 2-sided 95% CI of the differences will be reported.

Additional analysis details will be provided in the SAP.

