8.2.2 GABA and Glutamate Concentrations

The concentrations of GABA and Glu in the ACC will be obtained during MRS acquisition. The analyses will be descriptive by assessing the statistics for the concentrations of GABA and Glu by treatment group and visit (pre-treatment: Visit 2 fMRI scan and post-treatment: Visit 5). The change from baseline will be defined as the difference in concentration of GABA and Glu between Visit 2 and Visit 5 for each treatment group. The 2-sided 95% CI for the mean difference between treatment group and pre- and post-treatment will be also examined.

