1 INTRODUCTION

The purpose of this statistical analysis plan (SAP) is to ensure the credibility of the study findings by specifying the statistical approaches to the analysis of the data. This SAP covers the planned analyses of all data collected on the eCRFs, and will identify handling of data issues. The statistical analysis plan presented in this document will supersede the statistical analysis methods described in the clinical protocol. Any deviations/changes from the planned analyses described in this SAP will be identified, with justification, in the appropriate section of the clinical study report. This SAP is based on the clinical study protocol 810P204, version 3.0, dated 12 Apr 2019 and its associated electronic case report forms (eCRF).

2 **STUDY OBJECTIVES**

The primary objective is to evaluate the effect of SPN-810 treatment on brain activity in subjects aged 8-12 years with ADHD and IA using functional Magnetic Resonance Imaging (fMRI).

Secondary objectives are to evaluate the effect of SPN-810 treatment on:

- The functional connectivity between brain regions using resting-state fMRI (rs-fMRI)
- The concentration of neurotransmitters glutamate and gamma-aminobutyric acid (GABA) using Magnetic Resonance Spectroscopy (MRS)
- Safety of SPN-810

Tertiary objectives are to evaluate the following:

- Pharmacokinetics (PK) of Molindone
- Effect of SPN-810 treatment on the Clinical Global Impression-Severity (CGI-S) and -Improvement (CGI-I) scores
- Effect of SPN-810 on the Retrospective-Modified Overt Aggression Scale (R-MOAS) score.

3 **ENDPOINTS**

Primary Endpoint is the change in the whole brain in BOLD fMRI contrast in response to the PSAP task from Baseline (Visit 2) to Visit 5.

Secondary Endpoints are:

- Change in functional connectivity as reflected in the Fisher's Z-transformation of correlation coefficients between brain regions during rs-fMRI from Baseline (Visit 2) to Visit 5.
- Change in the concentrations of neurotransmitters GABA and glutamate in the anterior cingulate cortex (ACC) from Baseline (Visit 2) to Visit 5 as determined by MR spectroscopy.
- Safety endpoints:
 - 1) Adverse events.
 - 2) Safety scales (Simpson-Angus Scale, Barnes Akathisia Rating Scale [BARS], and Abnormal Involuntary Movement Scale [AIMS]).
 - 3) Clinical laboratory tests (hematology, chemistry, and urinalysis).

- 4) Vital signs.
- 5) Electrocardiograms (ECGs).
- 6) Columbia-Suicide Severity Rating Scale (C-SSRS).

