6.2 Handling of Dropout or Missing Data

No imputation will be implemented.

7 **STATISTICAL ANALYSIS**

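### SAP 7.5.1 never summarises the change in connectivity that SAP 3 names as the endpoint, and SAP 7.5.1, 7.5.2 and 7.7.2 drop the protocol's between-arm differences with 95% CIs

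*SAP*

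**What the plan says.** **Connectivity.** SAP 3 lists the endpoint as "Change in functional connectivity as reflected in the Fisher's Z-transformation of correlation coefficients between brain regions during rs-fMRI", from Visit 2 to Visit 5. SAP 7.5.1 instead takes the z-score at each visit as the variable and plans descriptive analyses to "assess the z-scores by treatment group (SPN-810 36 mg group and placebo) and visit (baseline and Visit 5"). It plans no Visit 5 minus Visit 2 value, no difference between arms and no interval.

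The protocol goes further. Its synopsis, under Secondary Analysis, says "Secondary endpoints will be the difference in the change in functional connectivity values" between the arms. Protocol 8.2.1 has the same by-arm, by-visit summary as the SAP. It then adds mean differences, SPN-810 minus placebo and post minus pre, and states that "the associated 2-sided 95% CI of the differences will be reported".

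**GABA and glutamate.** Protocol 8.2.2 says "The 2-sided 95% CI for the mean difference between treatment group and pre- and post-treatment will be also examined", and the synopsis has a matching sentence. SAP 7.5.2 keeps levels by arm and visit, and change by arm.

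**Behavioural scales.** For R-MOAS, CGI-I and CGI-S, protocol 8.4.2 sets a two-sample t-test (or a nonparametric analysis), the 36 mg minus placebo difference in means, and its 2-sided 95% CI. SAP 7.7.2 keeps observed values and change from baseline by arm.

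**Stated reasons.** SAP 1 gives the SAP precedence over the protocol's statistical methods. SAP 6.1 says that, because the study ended early, all analyses are descriptive and no hypotheses are tested. It lists n, mean, SD, median, minimum and maximum for continuous variables.

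**The concern.** Two things look wrong. First, the SAP defines an endpoint in section 3 and summarises a different quantity in 7.5.1. Early termination does not account for this, because the same SAP keeps change from baseline for GABA, glutamate and the scales.

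Second, the protocol's interval estimates have gone without mention. The protocol had already called the connectivity analysis exploratory and the GABA/glutamate analysis descriptive, and it still set CIs for both. Becoming descriptive is therefore not in itself a reason to remove them.

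At stake is whether a reader of the report can see the planned connectivity estimate and how imprecise it is. With few children per arm, by-arm means without an interval for the contrast do not show that imprecision directly.

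**Working it through.** The documents give no SD, effect size or power figure for these endpoints, so there is no stated number to reproduce. The check has three steps.

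**Step 1: what each document plans.**

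| Endpoint | Protocol | SAP | Missing from the SAP |
|---|---|---|---|
| Connectivity | 8.2.1: z-scores by arm and visit; differences between arms and post minus pre; 95% CI | 7.5.1: z-scores by arm and visit | Within-subject change, between-arm difference, CI |
| GABA, glutamate | 8.2.2: levels, change, 95% CI for the mean difference | 7.5.2: levels, change by arm | Between-arm difference, CI |
| R-MOAS, CGI-S, CGI-I | 8.4.2: test, difference in means, 95% CI | 7.7.2: observed values and change by arm | Between-arm difference, CI (and the test, which SAP 6.1 explains) |

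The sentence in protocol 8.2.1 can be read as two separate differences or as one difference in change; the synopsis supports the second reading. The SAP keeps neither.

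**Step 2: what can be rebuilt from the planned tables.** For a difference in mean change with n per arm and a common SD of change, the 95% half-width is t(0.975, 2n−2) × √(2/n) × SD of change. SAP 6.1 together with 7.5.2 and 7.7.2 supplies n, mean and SD of change by arm for GABA, glutamate, R-MOAS and CGI-S, so those intervals can be computed by hand. CGI-I has no Visit 1 value (SAP 5.4) and is itself a rating of change, so its by-arm table is enough.

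Connectivity is different. The variance of change is SD₂² + SD₅² − 2ρ·SD₂·SD₅, where ρ is the Visit 2 to Visit 5 correlation. The planned tables give the two SDs but not ρ.

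**Step 3: size.** Protocol 4.1 plans 15 per arm. The number left after early termination is not stated, so 10 and 5 are assumptions.

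Half-width in SDs of change:
- n = 15: 2.048 × √(2/15) = 2.048 × 0.365 = 0.748
- n = 10: 2.101 × √(2/10) = 2.101 × 0.447 = 0.940
- n = 5: 2.306 × √(2/5) = 2.306 × 0.632 = 1.458

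For connectivity, assume equal SDs at the two visits. Then SD of change ÷ single-visit SD = √(2(1−ρ)), which is 1.414, 1.183, 1.000 and 0.775 at ρ = 0, 0.3, 0.5 and 0.7. The values of ρ are assumptions. Multiplying gives half-widths in single-visit SDs:

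| n per arm | Visit 5 only | Change, ρ=0 | ρ=0.3 | ρ=0.5 | ρ=0.7 |
|---|---|---|---|---|---|
| 15 | 0.748 | 1.058 | 0.885 | 0.748 | 0.579 |
| 10 | 0.940 | 1.329 | 1.112 | 0.940 | 0.728 |
| 5 | 1.458 | 2.063 | 1.726 | 1.458 | 1.130 |

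The Visit 5 column can be computed from the tables SAP 7.5.1 plans. The change columns can only be bracketed: at 10 per arm, from 0.728 to 1.329 over this range of ρ.

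**The case against.** The strongest reply is that the narrowing is disclosed. SAP 6.1 cites early termination and lists the descriptive statistics to be used. Confidence intervals are not on that list, and SAP 1 gives the SAP precedence. This stands as an explanation for dropping the t-test in protocol 8.4.2. It does not settle the intervals: the SAP never says they are dropped, and the protocol's own list of descriptive statistics (7.1) is the same and stood alongside its CIs. Nor does it explain why change is missing for connectivity alone.

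Several stronger readings are tempting and should not be drawn.

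- *That the between-arm information is lost throughout.* It is not. For GABA, glutamate and the scales it can be rebuilt from planned summaries.
- *That without a difference in change no valid treatment comparison remains for connectivity.* Allocation is randomised 1:1, so the Visit 5 comparison between arms is also valid. On the figures above it is more precise than change when ρ is below 0.5.
- *That the two visit means come from different children.* The randomisation rule says "eligibility will minimally require completion of (1) two PSAP sessions and (2) the MPRAGE structural scan", which does not name the resting scan, and the SAP says "No imputation will be implemented". But SAP 7.5 uses the completed population, and SAP 7.1 requires imaging at baseline and post-treatment for it. Different children would contribute only if that definition does not cover the resting scan. The text leaves this open.
- *That the primary BOLD analysis was cut in the same way.* Protocol 8.1 and 8.1.1.1 set no CI for BOLD, so there is nothing to restore.

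**Conclusion.** The point holds in a limited form. SAP 7.5.1 does not summarise the endpoint that SAP 3 defines, and the SD of within-subject change and the CI for the difference in change cannot be recovered without assuming ρ. SAP 7.5.2 and 7.7.2 also omit the between-arm differences with 95% CIs set in the protocol, with little practical loss.

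If restored, the intervals would have half-widths of about 0.75 SD of change at the planned 15 per arm, 0.94 at 10 and 1.46 at 5. These figures assume equal arms and a common SD; the single-visit figures also assume equal SDs at both visits and a chosen ρ.

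Severity is minor: a conclusion of this small terminated trial is unlikely to turn on it. The benefit is that the SAP would analyse its own endpoint and state its imprecision.

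**What to change.** - **SAP 7.5.1:** add within-subject change in z-score (Visit 5 minus Visit 2) by arm, with n, mean and SD, for subjects who have both resting scans. Add the SPN-810 minus placebo difference in mean change with a 2-sided 95% CI and no p-value.
- **SAP 7.5.2 and 7.7.2:** restore the SPN-810 minus placebo difference with a 2-sided 95% CI and no p-value, in change from baseline (for CGI-I, in the rating itself).
- **All three sections:** state that the intervals are unadjusted for multiplicity and are for estimation only.
- **Study report:** SAP 6.1 describes the imaging data as already analysed. Identify the imaging additions as added analyses, with justification, by the route SAP 1 gives for changes.

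The cost is some wording and a few table entries from data already collected. The outside imaging group named in SAP 6.1 would have to supply subject-level changes or extra summaries. The downside is that several wide, unadjusted intervals will be shown, and the imaging ones will be post hoc.

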7.5.2 GABA and Glutamate Concentrations

The concentrations of GABA and Glu in the ACC will be obtained during MRS acquisition. The descriptive analyses will be used to examine the concentrations of GABA and Glu by treatment group and visit (pretreatment at Visit 2 fMRI scan and post-treatment at Visit 5). The change from baseline (Visit 5 – Visit 2) in concentration of GABA and Glu will also be assessed for each treatment group.

7.6 **Safety Analysis**

Evaluation of safety will be performed for the safety population. Safety data that will be evaluated include AEs, clinical laboratory results, vital signs, ECGs, and findings from the physical examinations. The occurrence of neurological side effects will be assessed by looking at any worsening in scores from Visit 1 to the end of the study visit for each of the Simpson-Angus Scale, Barnes Akathisia Rating Scale, and AIMS. Suicidal ideation and suicidal behavior will be measured by the C-SSRS.

All summary tables related to safety analyses will use the safety population.

7.6.1 Adverse Events

AEs will be classified into standardized medical terminology from the verbatim description (Investigator term) using the Medical Dictionary for Regulatory Activities (MedDRA V22.0). AEs will be summarized using discrete summaries at the subject and event level by system organ class and preferred term for each group of doses. Similarly, treatment-emergent AEs will be summarized by severity and relationship separately. Verbatim description and all MedDRA level terms, including the lower-level terms, for all AEs will be contained in the subject data listings.

All AEs occurring throughout the study period will be recorded. Treatment-emergent AEs (TEAEs) will be collected starting after the baseline fMRI scan and after the first dose of study medication (after Visit 3) to the end of the study. These AEs include those that emerge after the fMRI procedures and during treatment or worsen in severity during treatment. These AEs will be tabulated, listed, and analyzed.

Separate TEAE incidence tables will be presented for the 2 treatment groups. The incidence rates for all SADRs will also be summarized as described for all TEAEs.

In addition, these same tables will be presented by treatment period (Titration, Maintenance, and combined Titration and Maintenance periods). For the combined Titration and Maintenance periods, the incidence of TEAEs will also be presented by highest severity reported and the dose of study

medication at first occurrence. Listings (and tabular summaries, if warranted) of deaths, other SAEs, and other significant TEAEs, including TEAEs resulting in treatment discontinuation, will be provided.

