3.5 Treatment Phase (4 weeks)

3.5.1 Titration Period, Day 1 to Day 14

Subjects will be instructed to titrate to reach the maintenance dose over a period of 15 days, according to the dose titration schedule shown in Figure 1 and Figure 2. Dosing will begin at SPN-810, and increase to on Day 3, 9 mg/day on Day 5, on Day 8, on Day 11, and on Day 15.

3.5.2 Maintenance Period, (14 days) Day 15 to Day 28

Following dose titration, treatment will be maintained for 2 weeks at 36 mg/day SPN-810 or placebo.

At Visit 4, before the end of the Maintenance period, blood will be drawn for quantitative PK analysis. The morning dose of study medication will be administered in the clinic. The following PK samples will be collected: pre-dose (-30 minutes), and 2, 3, 4 and 6 hours post-dose (± 15 minutes).

At Visit 4, all subjects will also have the option to participate in an OLE study (Protocol 810P304) in which all subjects will receive active treatment. At the visit, subjects will receive a blinded conversion medication card that will adjust the subject's total daily dose to 18 mg SPN-810 for initiation into the OLE (Figure 1). Those subjects who do not elect to participate in this extension study will be tapered down prior to discontinuation of the study medication and will receive a taper down card at Visit 4 (Figure 2).

At Visit 5, subjects will return to the Imaging Center for the post-treatment fMRI/PSAP Task and will use (when applicable) the same Caseforge helmet used at Visit 2.

At the completion of the MRI scans (Visit 2 and Visit 5), subjects will be administered the questionnaire to validate their understanding of the task and to describe the characteristics of their opponent. The results of the questionnaire will be provided to the study site.

3.6 Taper/Conversion Phase (7 days), Day 29 to Day 35

Subjects will complete the 1-week Taper or Conversion phase.

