4.2 Schedule of Visits and Procedures

All subjects who have consented are required to follow the protocol procedures, regardless of the number of doses of study medication taken. The Sponsor, or the Sponsor's designee, must be notified of all deviations from the Schedule of Events and Procedures (Table 1), and these

procedures, if applicable, should be performed at the nearest possible time to the original schedule. Subjects will be instructed to call study personnel to report any issues or abnormal reactions during the intervals between study visits and to return to the study site if medical evaluation is needed, especially when urgent. Unscheduled visits may be conducted at the discretion of the Investigator throughout all study periods. The Medical Monitor must be promptly contacted in the event that any clinically significant findings or information is obtained during the unscheduled visit. For emergency and other unscheduled visits to a medical facility other than the study site, medical records will be obtained by the Investigator or qualified designee as source data for study follow-up by the Investigator.

Table 1: Schedule of Events and Procedures

Phase Pr		re-treatment		Treatment			Taper/Conversion
Period	d Screening Baseline Titration		Maint	enance	EOS		
VISIT NUMBER	1	2 ª	3		4 ^b	5ª	6°
Day	-30	-5	to 0	1-14	21	28	35
Window (days)	≤30d prior to titration	≤5d prior to titration		0	- 2/+1 d from titration	-/+ 1d from titration	7d±2d from Visit 5
Informed Consent/Assent ^d	Х						X
Inclusion/Exclusion Criteria	Х						
R-MOAS, MINI-KID, CGI-S, and Vitiello Scales	X				Xe		Xe
CGI-I Scale					Х		Х
Medical History and Demographic Data	Х		х				
Physical Examination	Х				Х		Х
ECG (12-lead)	Х				Х		X
Vital Signs	Х				Х		X
Hematology/Chemistry/ Urinalysis	X						Х
PK Blood Sampling					X		
Weight, Height, and BMI	Х				X		Х
Urine Drug Screen	Х						
Urine Pregnancy Test ^f	Х						X
Caseforge Scan	Х						

Phase	Pre-treatment			Treatment			Taper/Conversion
Period	Screening	Baseline		Titration	Maintenance		EOS
VISIT NUMBER	1	2 ^a	3		4 ^b	5ª	6°
Day	-30	-5 to 0		1-14	21	28	35
Window (days)	≤30d prior to titration	≤5d prior to titration		0	- 2/+1 d from titration	-/+ 1d from titration	7d±2d from Visit 5
Edinburgh Handedness Inventory		Х					
MRI Safety Questionnaire		Х				X	
Habituation Phase (Practice and Mock Scan)		Х				X	
MRI Session		Х				Х	
PSAP Questionnaire		Χ				X	
Columbia-Suicide Severity Rating Scale (C-SSRS)	X				Х		Х

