Safety Scales (Simpson-Angus, BARS, and AIMS)					х		Х
Adverse Events			Х		Х	Xi	Х
Concomitant Medication	Х		Х		Х	Xi	Х
Randomization			Χg				
Drug Compliance					X		X
Drug Dispensation			X ^j		X ^h		
Drug Return					X		Х

- a. The fMRI for Visit 2 and Visit 5 will be performed at the Imaging Center. At Visit 5 the fMRI will be schedule preferably in the morning 3 hours +/- 1 hour from the time the study medication was taken in the maintenance period.
- b. Subjects will decide if they will participate in the OLE
- c. Subjects who choose to participate in the OLE will consent at Visit 6.
- d. Written Informed Consent must be obtained prior to performing any study-related procedures.
- e. Only R-MOAS and CGI-S scale will be administered.
- f. To be performed for female subjects of childbearing potential
- g. Randomization will be performed by the study site once eligibility from the two PSAP fMRI sessions and structural scan are completed at the Imaging Center.
- h. Taper or Conversion kit will be dispensed.
- i. AEs and Con Meds will be recorded through a follow up call from the site
- j. Subjects will start their first dose the next day after dispensation (Day 1).

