4.2.3 Randomization/Visit 3, (Day 0)

The following procedures will be performed at the study site:

- 1. Randomization.
- 2. Record Concomitant Medications.
- Record Adverse Events.
- 4. Assess for any clinical significant changes in Medical History.
- 5. Dispense Study Medication

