4.2.4 Maintenance/Visit 4 (Day 21)

Visit 4 will occur 21 days after the start of the Titration period. Subjects will be instructed to take their morning dose at the site. The following procedures will be performed:

- 1. Administer CGI-I and CGI-S.
- Administer R-MOAS.
- 3. Record Vital Signs (Heart Rate [HR], Blood Pressure [BP], Temperature, and Respiration Rate [RR]).
- 4. Perform Physical Examination.
- 5. Record Height, Weight, and BMI.
- 6. Perform 12-lead ECG.
- 7. Collect blood samples for PK.
- 8. Administer C-SSRS.

- 9. Administer Safety Scales (Simpson-Angus, Barnes Akathisia Rating, and AIMS).
- 10. Record Adverse Events.
- 11. Record Concomitant Medications.
- 12. Assess Drug Compliance.
- 13. Drug Return.
- 14. Dispense Study Medication (Either Conversion or Taper dose based on subject's decision to participate in OLE.

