6.3.1.2 Recording and Evaluation of Adverse Events

All subjects who provided written Informed Consent (starting at Visit 1) will be questioned regarding the occurrence of AEs. Treatment emergent adverse events (TEAE) are undesirable events not present prior to study treatment/procedures, or an already present event that worsens either in intensity or frequency following the study treatment/procedure. A treatment emergent adverse event (TEAE) is an adverse event that occurs after study treatment/procedures has started. Adverse events occurring prior to the administration of the study medication/procedures (Day 1) will become part of the subject's

medical history including the severity of the event. At each visit, the Investigator must seek information on AEs by specific questioning and, as appropriate, by examination. Information on all AEs should be recorded immediately in the source document and also in the appropriate AE module of the eCRF. All clearly related signs, symptoms, and abnormal diagnostic procedures/laboratory results should be recorded in the source document, though they may be assessed as one diagnosis. For example fever, elevated white blood cells, cough, abnormal chest X-ray, etc., may all be reported as pneumonia.

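### TEAEs are to be tabulated by dose at first occurrence, but no adverse event enquiry is scheduled between Day 0 and Day 21, while the dose changes five times by Day 15

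*SAP*

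**What the plan says.** **Tables planned.** SAP 7.6.1, in the same terms as protocol 8.3.1, states that "these same tables will be presented by treatment period (Titration, Maintenance, and combined Titration and Maintenance periods"), and that for the combined periods "the incidence of TEAEs will also be presented by highest severity reported and the dose of study" medication at first occurrence.

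**Dosing.** Dosing starts on Day 1, the day after dispensation. Protocol 3.5.1 gives the changes as "on Day 3, 9 mg/day on Day 5, on Day 8, on Day 11, and on Day 15" (some dose values are redacted, the days are not), and Table 2 shows the same boundaries. Section 5.1.5 does not allow dose reduction.

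**Collection of adverse events.** Protocol 6.3.1.2 ties active enquiry to visits: "At each visit, the Investigator must seek information on AEs by specific questioning". In Table 1 adverse events are marked at Visit 3, Visit 4, Visit 5 (by a follow-up call from the site, footnote i) and Visit 6. The Titration column, Days 1 to 14, has no mark. Section 4.2.3 lists "Record Adverse Events" on Day 0, and the next listing is in section 4.2.4, where "Visit 4 will occur 21 days after the start of the Titration period".

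**Between visits.** Section 4.2 adds: "Subjects will be instructed to call study personnel to report any issues or abnormal reactions during the intervals between study visits". It also allows unscheduled visits. Under section 4.2.6, a subject who stops during Titration returns for a final visit within one week.

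**The concern.** A table by dose at first occurrence needs an onset date accurate enough to place each event in a step of two to four days. The site's first scheduled question about events on treatment comes after all of Titration is over. A parent asked on Day 21 when a child's drowsiness or restlessness began may well be a few days out, and a few days is a whole dose step.

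Two things are at stake. First, the by-dose table invites the reader to ask at which dose each event began. With about 15 children planned on active treatment, a handful of misdated events can alter a row. Second, events that were mild or brief during up-titration may not be remembered at all, in either arm.

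**Working it through.** The documents give no recall interval or dating accuracy, so there is no figure of theirs to reproduce. The check is a day count, followed by an illustration under stated assumptions.

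**Day count.** Step length = last day − first day + 1. Recall = day of Visit 4 − onset day. Inputs: step boundaries from protocol 3.5.1 and Table 2; Visit 4 on Day 21 with window −2/+1 from Table 1, that is Days 19 to 22.

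| Dose step | Length (days) | Recall to Day 21 | Recall over the window |
|---|---|---|---|
| Days 1–2 | 2 | 19–20 | 17–21 |
| Days 3–4 | 2 | 17–18 | 15–19 |
| Days 5–7 | 3 | 14–16 | 12–17 |
| Days 8–10 | 3 | 11–13 | 9–14 |
| Days 11–14 | 4 | 7–10 | 5–11 |

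Recall runs from 19 − 14 = 5 days to 22 − 1 = 21 days. For onsets spread evenly over Days 1 to 14 and Visit 4 on Day 21, the mean is 13.5 days. In every step the shortest recall exceeds the length of the step.

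**Fixed dating error.** Shift each of the 14 titration onset days by a fixed amount and count those that land in another step (dates before Day 1 are set to Day 1).

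| Error | Wrong step, dated early | Wrong step, dated late | Moved into Maintenance, dated late |
|---|---|---|---|
| 1 day | 4 of 14 | 5 of 14 | 1 of 14 |
| 2 days | 8 of 14 | 10 of 14 | 2 of 14 |
| 3 days | 11 of 14 | 13 of 14 | 3 of 14 |

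**Random dating error.** Assume onset uniform over the 14 titration days and a normal error with mean zero, applied only to events dated by recall. Simulation gives:

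| SD of dating error (assumed) | Wrong dose step | Of these, in the adjacent step | Moved into Maintenance |
|---|---|---|---|
| 1 day | 25% | 99% | 3% |
| 2 days | 46% | 91% | 6% |
| 3 days | 58% | 79% | 9% |
| 5 days | 71% | about 60% | 14% |

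A hand check agrees. The mean size of a late error, counting early errors as zero, is 0.399 × SD. Only the Day 15 boundary matters for the period split, so the share moved is about 0.399 × SD / 14: 2.9% at SD 1 and 14.3% at SD 5. For the dose step, four boundaries can be crossed from both sides and one from one side, nine in all. At SD 1 that gives 9 × 0.399 / 14 = 25.6%, slightly above the simulated value because an error that crosses two boundaries is counted twice.

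**Effect of phoned-in events.** If a share p of titration events is phoned in promptly and dated correctly, the wrong-step share becomes (1 − p) times the figure above. With p = 0.5 (an assumption), 25% to 71% becomes about 13% to 35%.

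**The case against.** The strongest reply is that the protocol does not leave Titration uncovered. Families are told to call the site with any problem, unscheduled visits are allowed, and a child who stops during Titration is seen within a week. Events caught in these ways are not dated from three-week recall. This stands, and it limits the point to the remaining events. It does not remove the point: call-in depends on the family judging an event worth a call, and mild or transient events are the least likely to prompt one.

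It is also true that dosing follows fixed days without reductions, so only the onset date has to be recalled. Under section 5.1.1 the kit has two Titration and two Maintenance cards of seven days each, so the change of period is also a change of card. That helps the period split. Within a card, the steps still depend on the date.

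The dating-error SD is assumed, and the result follows it closely. The SAP is descriptive throughout, the by-dose table informs only the active arm, and no endpoint or decision rests on it. All of this stands and keeps the point modest.

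Three stronger readings are tempting, and the documents do not support them:

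- *That the safety tables mainly reflect recall error.* At an SD of 1 or 2 days most recalled events stay in the right step, and TEAE incidence by arm over the combined periods does not use the step at all.
- *That the Titration/Maintenance split should go.* Under the same assumptions 86% to 97% of titration events stay in the right period.
- *That the schedule contradicts the 24-hour EPS reporting rule in protocol 6.3.2.2.* That clock starts when the site first becomes aware of the event, which is compatible with enquiry at visits plus call-in.

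Figures 1 and 2 are not shown, so they could not be checked for an extra contact. Table 1 and sections 4.2.3 and 4.2.4 list none.

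**Conclusion.** The point holds for the table by dose at first occurrence. It asks for onset dates finer than the schedule reliably supplies. For titration events that are neither phoned in nor followed by early stopping, recall of 5 to 21 days is set against steps of 2 to 4 days. The day count comes straight from the documents. The size of the misclassification does not: about 25% to 71% in the wrong step, mostly the neighbouring one, rests on an assumed SD of 1 to 5 days and evenly spread onsets, and falls in proportion to the share of events phoned in. The period split is affected far less, at about 3% to 14%. Under-recording of mild or transient events is plausible in both arms, but the documents do not allow it to be quantified.

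**What to change.** **In the protocol, for any subjects still to be treated or a later study of this design.** Add site calls within Titration to collect adverse events and concomitant medications. Section 4.2.5 and Table 1 footnote i already use such a call after Visit 5. Alternatively, dispense a dated caregiver adverse event card with the blister cards at Visit 3. Either way, record the onset date and the blister-card day for each event. The cost is a few minutes of site time per call or a printed card. The downside is that more minor events will be recorded, in both arms.

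**In the SAP, where collection can no longer change.** SAP 6.1 records that the study ended early. In SAP 7.6.1, drop the table by dose at first occurrence, or label it as based on retrospectively recalled onset dates. Keep the Titration/Maintenance tables with the same footnote, and keep the combined-period tables. This costs one table or one footnote.
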